# **Exploratory Hypotheses**

Additionally, we want to see if pre-post changes are correlated with a) adherence
(amount of breathwork practice, i.e., is there a dose response?), and b)
credibility/expectancy of the breathwork intervention given. We would expect both
greater adherence(in the coherent breathwork practice arm) and
credibility/expectancy to be associated with greater improvements on the outcome
measures listed.

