# Outcome measures

All outcomes (primary, secondary, other) are mentioned below. Pre-post intervention and follow-up questionnaires will be self-completed by participants online via the survey platform Qualtrics, which will be linked to Prolific. Three short scales will be used to measure outcomes of mental health, well-being and sleep disturbance at these timepoints (baseline/pre-intervention, post-intervention, 1-month follow-up): the Depression Anxiety Stress Scale (DASS-21) (Lovibond, & Lovibond, 1995), World Health Organisation- Five Well-Being Index (WHO-5) (WHO, 1998) and PROMIS Item Bank v. 1.0 - Sleep-Related Impairment - Short Form 8a (Hanish, Lin-Dyken & Han, 2017). The primary outcome will be stress (measured using the DASS-21 stress subscale), and the primary timepoint will be postintervention (four weeks post-randomisation). The secondary outcomes will be: anxiety and depression (from DASS-21) well-being (WHO-5) and sleep disturbance (PROMIS). Immediately after starting the breathwork, participants will be asked about the credibility/expectancy of the intervention randomly allocated to them to assess if the intervention and placebo are seen as equally credible and thus merit equal expectation of benefit. This will be measured using the 6-item Credibility/Expectancy Questionnaire (CEQ) (Devilly & Borkovec, 2000), which is another secondary outcome. The last secondary outcome, which will be measured post-intervention, is: adherence (number of times participants self-reported practicing breathwork out of the 28days assigned). Other outcomes include an open-ended question on participants overall experiences of the protocol and/or study period. Pre-intervention, simple demographics (Age, Gender and Ethnicity) will be collected and, post-intervention/follow-up, participants will be asked if anything impaired their ability to perform the breathwork, and if they can guess the study hypothesis (to tentatively see if blinding was successful—see Procedure section).

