# Secondary Outcome Measures:

- 2. Subjective anxiety (DASS-21 anxiety subscale)
- 3. Subjective depressive symptoms (DASS-21 depression subscale)
- 4. Subjective wellbeing (WHO-5)
- 5. Subjective sleep disturbance (PROMIS-8a)

All of above outcomes measured pre-post-follow-up.

- 6. Self-reported credibility and expectancy of protocol (CEQ-6) . Measured after completing first session of breathwork.
- 7. Self-reported adherence to breathwork protocol (number of sessions participants self-report practicing out of 28 days assigned). Measured post-intervention.

Other—Overall experience, Impairment of practice, Hypothesis guessing, Attention checks
Optional open-ended questions on participants' perspectives and overall experience of the
protocol (post-intervention) / study-period (follow-up), whether anything impaired
participants' ability to perform their randomly allocated breathwork (post-intervention), and
if they can guess the hypothesis of the study (follow-up). Lastly, The DASS, WHO, and

PROMIS will all have one attention-check question in them to ensure participants are completing the surveys properly.

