# Intervention and Comparator

Both groups will also be provided with an identical ~5min introductory/welcome audio to the study which they can listen to on the first day.

Participants in intervention group will be randomised to a guided audio of coherent breathing (at ~5.5.bcpm with equal inhales/exhales of ~5.5secs each without deliberate pauses), for 28days (4weeks), pre-recorded by a trained breathwork facilitator, delivered remotely online. The average coherent breathing rate for maximising HRV is around 5.5bcpm so this cadence was chosen for the intervention group. The duration of ~10min was deemed as a manageable time for participants, and several studies (ranging from days to weeks) on meditation have shown benefit can be derived from this short length of practice.

Participants in control group will be randomised to a guided audio of placebo 'sham' coherent breathing breathwork (12bcpm with equal inhales/exhales of 2.5secs each without deliberate pauses) for ~10mins/day, for 28days (4weeks), pre-recorded by a trained breathwork facilitator, delivered remotely online. The metric of 12bcpm is in line with guidance from the British Journal of Nursing, Royal College of Physicians, and Johns Hopkins University which state that the average, healthy bcpm should range from: 12-18bcpm, 12-20bcpm, and 12-16bcpm, respectively, hence we chose the minimum for the control group.

12 bcpm is highly unlikely to be difficult or detrimental to anyone based on BJN, RCP, and JHU guidance as it is at the lower bound of bcpm for typical resting breathing for adults.

The intervention/control audios are identical (exact same sound and instruction). The placebo control is matched to the active intervention in all domains but pace of breathing.

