### Randomisation and blinding

The type of study is participant blinded RCT with assessor blinded data collection (that is assessor is not present for data collection which is self-completed by the participant on a survey software platform). After completing the pre-intervention survey, participants will be randomly assigned, via the online survey software Qualtrics using block randomisation (1:1), to receive either the intervention coherent breathing breathwork (5.5bcpm), or placebo coherent breathing breathwork (12bcpm). Participants will be blinded to their intervention (concealment)—the technique of breathwork will be referred to as 'rhythmic breathing' in both the active intervention and placebo control breathwork audios, in an attempt to blind participants to the intervention being used.

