Intention-to-treat; using an independent t-test to see if there is a difference. Post-intervention is the primary timepoint for primary outcome stress. For both the primary outcome and secondary scale outcomes, group x time effects at the p<.05 level will be determined using mixed ANOVAs. Group x time effects at the p<.05 level will be followed up with simple contrasts (with pre-intervention as the comparator) and Bonferroni-corrected within-group t-tests. Baseline data will be controlled for depending on the outcome being tested (i.e., DASS Stress at baseline will be entered as a covariate when testing effects on DASS Stress). Data analysis will be performed in R and SPSS.

Secondary analysis

Per-protocol analysis (participants completing at least 14 sessions [50%] of the breathwork) will be conducted as secondary analysis.

Sensitivity checks

If sizeable missing data are present (greater than 5%), they will be replaced using multiple imputation, and used for sensitivity analysis. Analysis without baseline covariates will be included as sensitivity analysis. The DASS, WHO, and PROMIS all have one attention-check question in them to ensure participants are completing the surveys properly. If a participant answers more than one incorrectly at each timepoint their data will be excluded from the main analyses but included in a sensitivity analysis. The same applies to those who state that their breathwork practice was significantly impaired in response to the question on impairment of practice below.

Exploratory analysis of secondary measures (quantitative)

Adherence to breathwork protocol

Post-intervention, participants will answer how many times they completed the guided breathwork out of the assigned 28 days. This will be compared between groups via unpaired t-test, and correlated with outcome scale scores on DASS, WHO and PROMIS within each condition to see whether there are any associations between adherence and changes in these scale scores. Adherence will be looked at as a moderator.

Credibility/expectancy of breathwork protocol

Similar to adherence, CEQ scores will be correlated with the outcome scale scores above, to see whether there are relationships between CEQ and changes in these scale scores within each condition. CEQ scales will be compared between groups via unpaired t-tests. If there are significant differences between groups on credibility/expectancy, it will be used in covariance analysis.

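### The SAP's exploratory rule lets credibility/expectancy, rated after exposure to the allocated pace, become a covariate when the arms differ on it, without saying that the estimate without it stands

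*SAP*

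**What the plan says.** The rule is in the SAP, in the paragraph on credibility/expectancy, which falls under the heading for exploratory analysis of secondary measures. The arms are compared first: "CEQ scales will be compared between groups via unpaired t-tests". Then: "If there are significant differences between groups on credibility/expectancy, it will be used in covariance analysis". The sentence does not say which outcome or model takes the covariate, or what becomes of the estimate without it.

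On timing, the protocol (Randomisation and blinding) states: "After completing the pre-intervention survey, participants will be randomly assigned". The CEQ comes later. The list of secondary outcome measures has it "Measured after completing first session of breathwork". The Outcome measures narrative says "Immediately after starting the breathwork, participants will be asked about the credibility/expectancy of the intervention randomly allocated to them". The two wordings differ, but under both the participant has already begun the allocated breathwork.

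On what separates the arms, the protocol (Intervention and Comparator) says: "The placebo control is matched to the active intervention in all domains but pace of breathing". Under Exploratory Hypotheses it expects "credibility/expectancy to be associated with greater improvements on the outcome" measures.

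The SAP's Primary analysis section is intention-to-treat (ITT). The only covariate it names is the baseline value of the outcome being tested.

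**The concern.** Covariate adjustment in a randomised trial is safe for measures that treatment cannot have changed. The CEQ is not one of these. A participant who has just breathed at 5.5 or 12 cycles per minute may rate credibility and expectancy partly on how that session felt. Both arms share the introduction, the label and the instructions, so a systematic difference in CEQ would probably reflect pace.

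The rule treats such a difference as an imbalance to be removed. The adjusted contrast then answers a different question (the arm difference at equal CEQ) from the protocol's primary hypothesis, which concerns the effect of the assigned practice. The bias can go either way: it attenuates the effect if slow breathing is rated more credible and inflates it if slow breathing is rated less credible. Because a significance test decides whether CEQ enters, the model also depends on the data, and CEQ enters most often when the shift is large.

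**Working it through.** **Inputs from the documents.** Alpha 0.05, power 0.80, d=0.35 and 260 needed (protocol, Participants); 1:1 allocation.

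**Inputs assumed.** a = true arm difference in CEQ, in within-arm SDs. b = within-arm slope of outcome on CEQ, in SDs. The documents give neither. Outcomes are oriented so that higher means greater improvement. One CEQ scale is used as the trigger.

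**Step 1: reproduce the plan's sample size.** A two-sided two-sample t-test at d=0.35 needs 130 per arm, 260 in total, with power 0.803. This matches the protocol. (The normal approximation gives 258; a one-sided test would need 202.)

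**Step 2: when does the rule apply?** The standard error of the CEQ difference at 130 per arm is sqrt(2/130) = 0.124. The smallest significant difference is about 1.97 × 0.124 = 0.244 SD.

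**Step 3: effect of adjusting.** If CEQ is in the model, the arm effect becomes d − a·b. With a=0.35 and b=0.3 this is 0.35 − 0.105 = 0.245, so 30% of the total effect is removed.

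**Step 4: mean estimate under the rule.** CEQ enters only when its observed difference D is significant, so the mean is d − b·E[D; |D|>0.244]. For a=0.3, z = (0.3 − 0.244)/0.124 = 0.45, and E = 0.3 × 0.674 + 0.124 × 0.360 = 0.247 (the other tail is negligible). With b=0.3 the mean is 0.35 − 0.3 × 0.247 = 0.276. The other rows follow in the same way. Trigger rates and power come from simulation at 130 per arm.

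| CEQ shift a | slope b | rule triggered | mean estimate | power (about 80% without CEQ) |
|---|---|---|---|---|
| 0 | 0.3 | 5% | 0.35 | about 80% |
| 0.1 | 0.2 | about 12% | 0.34 | 79% |
| 0.3 | 0.2 | about 68% | 0.30 | about 68% |
| 0.3 | 0.3 | about 68% | 0.28 | about 62% |
| 0.4 | 0.3 | about 90% | 0.24 | about 49% |
| -0.3 | 0.3 | about 68% | 0.42 | inflated by the bias |

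**Step 5: no true effect.** With d=0, a=-0.3 and b=0.3, the mean estimate is 0 + 0.3 × 0.247 = 0.07 in favour of coherent breathing, and false positives rise from 5% to about 10%.

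**Step 6: does CEQ have to be causal?** No. Suppose CEQ has no effect on outcome but both load 0.5 on an unmeasured cause. The within-arm slope is then 0.5 × 0.5 = 0.25, and with a=0.35 the adjusted effect is 0.35 − 0.35 × 0.25 = 0.26. If a=0, nothing is removed on average.

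**The case against.** The strongest reply is where the rule sits. It is exploratory, and the primary analysis names only the baseline outcome as covariate. A reader might infer that the primary stress result will be CEQ-adjusted, and so that the trial's planned 80% power is at risk. The documents do not say so, and the power column above describes only a comparison to which the rule is applied. This part of the objection stands.

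Several further points also have force:

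- The protocol hypothesises no CEQ difference between arms and matches them on everything but pace, so the shift may be small. With a shift of 0.1 SD or none, the estimate hardly moves. A trigger by chance alone leaves it unbiased on average.
- A reader might infer that any CEQ difference must come from pace. That is too strong. It may be chance. Each condition also has its own CEQ survey, sent after allocation (protocol, Procedure), so differential completion could produce one.
- Asking what remains of the effect net of expectancy is a legitimate question in a placebo-controlled trial.

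These points limit the reach of the concern but do not remove it. The sentence does not tie the adjustment to an exploratory model or say that the ITT estimate without CEQ holds whatever the CEQ tests show, so it could be applied to any group comparison. Simple covariance adjustment on a post-exposure rating separates expectancy from pace only under strong assumptions, and the SAP states none.

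**Conclusion.** The point holds in a limited form. The SAP states a significance-triggered rule that conditions a treatment comparison on a measure the treatment can change, and it leaves the scope of that rule open. It does not show that the primary result will be affected.

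Under the assumed shifts and slopes, the mean estimate ranges from essentially the planned 0.35 down to 0.24, or up to 0.42 if slow breathing is rated less credible. It would be wrong to conclude that the bias always runs against coherent breathing. All these figures rest on 130 analysed per arm, a total effect of 0.35, one triggering scale, and values of a and b that the documents do not supply. The direction and mechanism do not depend on the exact values; the size does.

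This should be corrected before analysis. It is a wording defect, not a failure of the design.

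**What to change.** Replace the sentence in the SAP's credibility/expectancy paragraph with:

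> CEQ is measured after randomisation and exposure and will not be a covariate in the primary or secondary treatment comparisons. The ITT estimates adjusted only for the baseline value of the outcome are the main results whatever the CEQ comparisons show. Any CEQ-adjusted or mediation model will be reported as exploratory, irrespective of the significance of the CEQ difference, with its no-unmeasured-confounding assumption stated.

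This keeps the expectancy question, removes the data-driven trigger, and leaves the SAP's analysis without baseline covariates as a sensitivity analysis. The protocol's two descriptions of CEQ timing could be aligned at the same time, although the point does not depend on it.

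The cost is SAP wording only, with no new data. The downside is that a CEQ difference can no longer be adjusted out of the main comparisons and must be discussed as a possible mechanism or source of bias.
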